#### **5.7.6 Sample size calculation**

In this study, a total sample size of 24 participants will be used, allocated equally into two groups of 12 participants each. Based on the recommendation by Julious, a sample size of 12 subjects per group is considered adequate to achieve reasonable precision for preliminary estimates in a pilot study.

### 5.7.7 Sampling

- None

### 5.7.8 Study variables and their definition

Independent variables

- Technique of vaccination: subcutaneous vs. intradermal
- Sex
- Age

Dependent variables

- ELISA: Antibody level for dengue at day 0, 30, 120
- ELISpot: T cell responses against dengue antigens at day 0, 30, 120
- Adverse event following vaccine (AEFI)

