## 5.4 Objectives

### Primary Objectives

1. To evaluate the antibody response to dengue virus following administration of the second dose of QdengaTM via the intradermal route.
2. To evaluate the T-cell response (CD4 and CD8) to dengue virus following administration of the second dose of QdengaTM via the intradermal route.

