## 5.6 Conceptual framework

A new dengue vaccine, Qdenga™, has recently become available in Thailand. As a live-attenuated vaccine, it does not require pre-vaccination serological screening for dengue immunity, unlike Dengvaxia™. However, access to Qdenga™ remains limited due to its high cost and the fact that it is not yet reimbursable for the general population. The vaccine is designed for subcutaneous administration and is given as a two-dose series, with the second dose administered three months after the first.

In theory, intradermal administration may elicit comparable immune responses while using a lower vaccine dose, owing to the high density of antigen-presenting cells in the dermal layer. Based on this rationale, investigators from multiple departments within the Faculty of Medicine have initiated a collaborative study to evaluate the immunogenicity and safety of intradermal Qdenga™ administration in healthy volunteers. Immune responses will be assessed at baseline, 30 days after the first dose, and 30 days after the second dose. All participants will receive the first dose subcutaneously as per standard practice, then be randomized to receive the second dose either subcutaneously or intradermally.

This study aims to enhance understanding of the immune response elicited by Qdenga™ given via different administration routes and to generate data that may inform future vaccine implementation strategies and potential dose-sparing approaches.

CONSORT FLOW Diagram

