### 5.7.9 Questionnaire/Instrument/Tool/Machine

#### Immunological study

##### Blood collection

- 15 ml of blood samples were taken before booster vaccination then 30 days after vaccination. The blood was split into 1 clotted blood tube and 2 heparinized tubes.

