##### Sample preparation

- The sample preparation process will be done in the Biosafety Level 2. Laboratory staff will wear adequate PPEs as per BSL2 protocol.
- The samples will always be opened in BSL2 cabinet.
- The heparinized blood was spun as per PBMC separation protocol. The PBMCs were stored in liquid nitrogen for further experiments while the plasma samples kept at -80 c as well as serum from clotted blood.
- Leftover samples will be kept for 5 years for relevant immunological analysis then will be discharge as per BSL 2 protocol.

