## Study flow

## Study procedure

Study period	Screening	Treatment	Treatment	Follow up	
		Vaccine dose 1	Vaccine dose 2	Day 30 ± 3 day	Day 120 ± 3 days
Day/week	Day 0 to -7	Day 0	Day 90 ± 3 days	Day 30 ± 3 day	Day 120 ± 3 days
Informed consent, medical history	X				
Contraceptive counselling	X				
Screen dengue IgG	X				
Review of Inclusion/exclusion criteria		X	X		
Physical examination		X	X		
Body Weight/ Height/ Vital sign		X	X		
Concomitant medication check		X	X		

Blood collection*		X	X		X
Randomization		X			
Vaccination		X	X		
Adverse event check (also by google form+/- telephone at 7, 30 day after each vaccination)		X		X	X

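### The immune outcomes are listed at Days 0, 30 and 120 but blood is marked at Days 0, 90 and 120, so Day 30 has no marked sample and the pre-dose-2 sample has no stated use

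*Combined protocol and SAP*

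**What the plan says.** - **Outcome list.** Section 5.7.8 gives "ELISA: Antibody level for dengue at day 0, 30, 120" and "ELISpot: T cell responses against dengue antigens at day 0, 30, 120".
- **Conceptual framework.** Section 5.6 matches this: "Immune responses will be assessed at baseline, 30 days after the first dose, and 30 days after the second dose". Dose 2 falls on Day 90, so these times are Days 0, 30 and 120.
- **Schedule.** In the table under Study procedure (section 5.7.10), the row "Blood collection" is marked at Day 0, Day 90 and Day 120. At Day 30 only the adverse-event check is marked, and that row allows contact by online form or telephone.
- **Methods text.** The blood collection paragraph of section 5.7.9 says "15 ml of blood samples were taken before booster vaccination then 30 days after vaccination". It names no Day 0 draw and does not say which dose the 30 days follow.
- **Storage.** PBMCs, plasma and serum are stored, and "Leftover samples will be kept for 5 years for relevant immunological analysis".
- **Objective.** The first primary objective in section 5.4 is "To evaluate the antibody response to dengue virus following administration of the second dose" by the intradermal route. The second asks the same of the T-cell response.
- **Analysis.** Section 5.7.12 lists two-sample tests for quantitative data. It mentions neither a baseline nor any adjustment.

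**The concern.** The outcome list and the sampling schedule do not describe the same study. A site that follows the visible schedule collects nothing at Day 30, which is a listed time point for both primary immune outcomes, and a missed Day 30 sample cannot be obtained later. The same site does collect a Day 90 sample that no visible section lists as an outcome or uses in the analysis.

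Day 90 matters because dose 2 is the only dose that differs between the arms and is the subject of both primary objectives. Everyone enters dengue IgG positive (section 5.7.3.1), everyone has had a subcutaneous first dose, and both arms receive a second dose. Similar Day 120 values in the two arms would therefore not show whether either second dose raised the response. A change from Day 0 to Day 120 mixes the two doses. A change from Day 30 to Day 120 includes 60 days before dose 2 was given. Only Day 90 to Day 120 isolates the dose-2 change within a person.

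**Working it through.** **1. Matching the days.** The plan states no figure on this point, so the check is a comparison of sets.

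| Source | Day 0 | Day 30 | Day 90 | Day 120 |
|---|---|---|---|---|
| 5.7.8, ELISA and ELISpot | listed | listed | – | listed |
| 5.6 | listed | listed | – | listed |
| Study procedure, blood row | marked | – | marked | marked |
| 5.7.9, blood collection | – | dose not stated | pre-booster | dose not stated |

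The column reading is supported by other rows. Vaccination is marked at Days 0 and 90 only, as a two-dose design requires. The adverse-event check is blank at Day 90 and marked at Days 30 and 120.

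**2. Counting samples** (24 participants, section 5.7.6).

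- Listed outcomes: 24 × 3 = 72 samples per assay.
- Covered by marked draws (Days 0 and 120): 24 × 2 = 48.
- Left over: 24 Day 30 results with no marked draw, and 24 Day 90 draws with no listed outcome.

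**3. Precision at Day 120 (illustration).** Inputs are 12 per arm (section 5.7.6), equal SDs, and a correlation r between the earlier value and Day 120. The documents give no r, so 0.3, 0.5 and 0.7 are assumed. Results are 95% CI half-widths in SD units.

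- Unadjusted: t(0.975, 22) × √(2/12) = 0.847.
- Adjusted for one earlier value: t(0.975, 21) × √(2/12) × √(1 + 1/20) × √(1 − r²). The factor √(1 + 1/20) allows for expected chance imbalance.

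| r | Adjusted between-arm half-width | Within-arm Day 90 to 120 half-width |
|---|---|---|
| 0.3 | 0.830 | 0.752 |
| 0.5 | 0.753 | 0.635 |
| 0.7 | 0.621 | 0.492 |

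The last column is t(0.975, 11)/√12 × √(2(1 − r)). Adjustment breaks even at r of about 0.23.

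The adjusted figures apply to Day 0 as a covariate just as much as to Day 90. The gain from using Day 90 instead of Day 0 is:

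- none if the two correlations are equal;
- 0.830 − 0.753, about 0.08 SD, for r of 0.3 (Day 0) and 0.5 (Day 90);
- 0.753 − 0.621 = 0.13 SD for 0.5 and 0.7;
- 0.830 − 0.621 = 0.21 SD for 0.3 and 0.7;
- negative if Day 0 correlates more strongly.

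A simulation of 20,000 trials gave root-mean-square half-widths within 0.002 SD of these values.

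**4. Day 30 as a substitute baseline (illustration).** Apparent change = true dose-2 rise + drift from Day 30 to Day 90. Take a true rise of 0.5 SD and an assumed decline of 0.25 to 0.5 SD before dose 2. The apparent rise is then 0.5 − 0.25 = 0.25 SD down to 0.5 − 0.5 = 0 SD.

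**The case against.** The strongest reply is that the disputed row carries an asterisk whose note is not visible, the flow diagrams are missing, and the table's columns are out of time order. A footnote on that row is exactly where a Day 30 draw, or the purpose of the dose-2 draw, might be stated. This stands as a limit on certainty about Day 30. It does not remove the point, because a Day 30 footnote would not put Day 90 into the outcome lists of sections 5.6 and 5.7.8.

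Other parts of the reply also carry weight:

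- Section 5.7.9 speaks of a booster without defining it as dose 2, so its support for a Day 90 draw is an inference.
- The randomised comparison at Day 120 is valid without Day 90. Adjusting for it in a 24-person pilot is an improvement, not a repair of that comparison.
- All correlations and the Day 30 to Day 90 decline are assumed. The plan does not propose a Day 30 to Day 120 change, and drift before dose 2 would on average cancel between arms. Step 4 above therefore concerns only the within-arm reading.
- The Day 90 blood is drawn on the visible schedule and material is stored, so the result is recoverable.

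What the reply leaves untouched is the contradiction between listed outcomes and marked draws, and the absence of any stated use for the one sample that speaks directly to the dose-2 change.

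**Conclusion.** The point holds, should be fixed, and is held with medium confidence because the footnote and flow diagrams could not be read. On the visible text, one of three listed time points for both primary immune outcomes has no marked sample (24 of 72 per assay), and 24 scheduled pre-dose-2 samples have no listed use. These counts rest only on the planned 24 participants and the table as it reads.

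The main consequence is that the baseline for the dose-2 response is undefined and could be chosen after the data are seen. Precision is secondary. Adjusting for an earlier value could narrow the Day 120 half-width from 0.85 SD to between 0.83 and 0.62 SD at the assumed correlations, but the part of that gain specific to Day 90 is unknown and could be nil or negative.

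**What to change.** 1. Read the footnote to the blood row and the flow diagrams in the full protocol. Then reconcile sections 5.6, 5.7.8 and 5.7.9 with the schedule table, naming every draw by study day in 5.7.9.
2. Keep the Day 90 draw and list it in 5.6 and 5.7.8 as an ELISA and ELISpot time point, taken before dose 2.
3. State in 5.7.12 that Day 90 is the baseline for the dose-2 response. Compare arms at Day 120 adjusted for it, on the log scale for antibody. For ELISpot use a pre-stated scale or a rank method, because background subtraction can give zero or negative values. Report the Day 90 to Day 120 change within each arm with a 95% CI.
4. For Day 30, add the draw to the schedule or remove the day from the outcome list. If the footnote already provides a draw, marking the table is enough. Removing Day 30 gives up the post-dose-1 assessment that 5.6 plans, so this should be a deliberate choice.

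**Cost.** A protocol amendment, since listed outcomes change. Day 90 needs no new draw on the visible schedule; if its assays were not budgeted, up to 24 further ELISA and 24 further ELISpot sample sets. Keeping Day 30, if it is not already provided for, adds one 15 ml draw for each of 24 participants, at a time point where only an adverse-event check is now marked.

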### 5.7.9 Questionnaire/Instrument/Tool/Machine

#### Immunological study

##### Blood collection

- 15 ml of blood samples were taken before booster vaccination then 30 days after vaccination. The blood was split into 1 clotted blood tube and 2 heparinized tubes.

##### Sample preparation

- The sample preparation process will be done in the Biosafety Level 2. Laboratory staff will wear adequate PPEs as per BSL2 protocol.
- The samples will always be opened in BSL2 cabinet.
- The heparinized blood was spun as per PBMC separation protocol. The PBMCs were stored in liquid nitrogen for further experiments while the plasma samples kept at -80 c as well as serum from clotted blood.
- Leftover samples will be kept for 5 years for relevant immunological analysis then will be discharge as per BSL 2 protocol.

##### Antibody analysis

- Detection of dengue-specific human Abs by ELISA
- Mixtures of all four DENV serotypes were captured onto a MAXISORP immunoplate (NUNC) coated with mouse anti-E antibody (4G2) or anti-NS1 antibody (NS1-F3). DENV captured wells were then incubated with B cell line (BCL) culture supernatants followed

by alkaline phosphatase (AP)-conjugated anti-human IgG Abs. The reaction was visualized by the addition of PNPP substrate. The reaction was stopped with NaOH.

### **T cell responses**

#### ELISpot assay

Briefly, PBMCs were added to polyvinylidene difluoride-backed plates (Millipore) precoated with a monoclonal antibody to IFN- $\gamma$  (1-DIK; MABTECH). Peptides were then added at a final concentration of 10  $\mu$ M and the PBMCs were cultured overnight. Cells were discarded and spots were revealed by incubation with biotinylated monoclonal antibody to IFN- $\gamma$  (MABTECH) followed by streptavidin-conjugated alkaline phosphatase and substrate. The spots were counted using an AID-ELISpot Reader (Autoimmun Diagnostika). The number of specific T-cell responders was calculated after subtracting negative control values.

#### **Peptides**

[figure not shown]
- 15-mer peptides overlapping by 5 amino acids corresponding to sequences of dengue serotype 2 strain 16681 (CprM, E, NS1, NS2, NS3, NS4, and NS5) and to the NS3 sequences of dengue serotype 1 strain Hawaii, dengue serotype 3 strain H87, and dengue serotype 4 strain H241 were synthesized to >80% purity (Sigma Aldrich). Lyophilized peptides were resuspended in dimethyl sulfoxide (DMSO; Sigma) at 80 mg/mL for peptide mixtures. The overlapping peptides were grouped together in pools corresponding to individual dengue proteins (dengue 2: CprM-26, E-97, NS1-71, NS2-70, NS3-123, NS4-70, NS5-95, dengue 1 NS3-124, dengue 3 NS3-124, and dengue 4 NS3-124). The final concentration of any single peptide was 2  $\mu$ g/mL, and the final concentration of DMSO was <1% in all experiments.

#### **5.7.10 Data collection**

- Participant information will be recorded in a case record form (CRF). Personal identifiers such as name, address, date of birth, and national identification number will not be recorded. Only the hospital number will be documented for follow-up purposes, and this will be removed and replaced with a study code when transferred into the electronic database. All paper CRFs will be stored in a locked cabinet until the completion of the study.

- Immunological study data will be analyzed and stored in electronic files. The linkage between laboratory results and participant information will occur only at the final stage of the study.

## Study flow

## Study procedure

Study period	Screening	Treatment	Treatment	Follow up	
		Vaccine dose 1	Vaccine dose 2	Day 30 ± 3 day	Day 120 ± 3 days
Day/week	Day 0 to -7	Day 0	Day 90 ± 3 days	Day 30 ± 3 day	Day 120 ± 3 days
Informed consent, medical history	X				
Contraceptive counselling	X				
Screen dengue IgG	X				
Review of Inclusion/exclusion criteria		X	X		
Physical examination		X	X		
Body Weight/ Height/ Vital sign		X	X		
Concomitant medication check		X	X		

Blood collection*		X	X		X
Randomization		X			
Vaccination		X	X		
Adverse event check (also by google form+/- telephone at 7, 30 day after each vaccination)		X		X	X

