Another study evaluated the safety and immunogenicity of an early low-dose tetravalent dengue vaccine candidate (LD-TDV), which uses an attenuated serotype 2 backbone, administered intradermally either with an injector device (PharmaJet) or a needle-syringe in 67 subjects. The findings indicated that the intradermal administration of LD-TDV was well tolerated, with no significant safety concerns, and induced an immune response against all four dengue serotypes. The overall tetravalent seroconversion rates were 13.8% at Day 28 and 31.0% at Day 118, comparable to the previously reported 25% seroconversion rate for low-dose TDV given intradermally in 72 flavivirus-naive adults. Local reactions, such as induration (91.7% vs. 12.5%;  $P < .0001$ ) and pruritus (50% vs. 8.3%;  $P = .0034$ ), were more frequent following intradermal vaccination compared to subcutaneous administration. Most of these reactions were mild and resolved within one day.

This study aims to ensure the safety of vaccine recipients by comparing the administration of a second dose via the intradermal (ID) route after an initial subcutaneous (SC) dose with a control group receiving both doses subcutaneously (SC-SC). Previous research in Thailand on COVID-19 vaccines also evaluated the safety and immunogenicity of fractional (1/5th or 1/6th) doses of homologous ChAdOx1 or BNT162b2 administered intradermally following an initial intramuscular (IM) dose, demonstrating safety and immunogenicity. Based on this, the study hypothesizes that intradermal administration of fractional doses of the Qdenga vaccine after an initial SC dose will be immunogenic and have acceptable systemic adverse effects, with potential utility as a booster in the future.

The potential of intradermal vaccination to maintain or enhance immunogenicity while reducing the required dose has been highlighted in several reviews. This method could lower costs and improve vaccine accessibility in low-resource settings. However, further research is needed, as no randomized studies have yet evaluated both humoral and cell-mediated immune responses to intradermal Qdenga vaccination.

[figure not shown]

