#### 5.7.3.2 Exclusion criteria

1. Have a medical history or family history of convulsion, epilepsy, encephalopathy and psychosis.
2. Be allergic to any component of the research vaccines or used to have a history of hypersensitivity or serious reactions to vaccination.
3. Women with positive urine pregnancy test, pregnant or breast-feeding, or have a pregnancy plan within six months.
4. Have acute infectious diseases, including dengue infection
5. Have severe chronic diseases or condition in progress cannot be controlled.  
For example, poor controlled DM and uncontrolled HT.
6. Have the history of urticaria 1 year before receiving the investigational vaccine.
7. Have needle sickness.

8. Have the history of immunosuppressive therapy, cytotoxic therapy or systemic corticosteroids
9. Have received blood products within 6 months before injection of investigational vaccines.
10. Not be able to follow the protocol or not be able to understand the informed consent according to the researcher's judgment, due to various medical, psychological, social or other conditions.
11. Recent administration within 1 months or planned to get any live attenuated vaccine within the study period.

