#### **5.7.4 Subject withdrawal criteria**

1. The participant chooses to withdraw from the study at any time.
2. The study is discontinued at the discretion of the investigator if continuation poses a potential risk to the participant.
3. The participant wishes to receive other vaccines (e.g., pneumococcal vaccine, zoster vaccine) within 30 days after receiving the study vaccine.
4. The participant develops anaphylaxis or any severe adverse event following the first dose of the vaccine.

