### Arms and Interventions:

Arm 1: subcutaneous Qdenga for 1st vaccination then intradermal Qdenga for 2nd vaccination

Arm 2: subcutaneous Qdenga for 1st vaccination then subcutaneous Qdenga for 2nd vaccination

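### Randomisation is scheduled at Day 0, about 90 days before the arms first differ, and no supplied text says when allocation is disclosed; randomising or unsealing just before dose 2 is a cheap improvement

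*Combined protocol and SAP*

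**What the plan says.** The Study procedure table marks the row "Randomization" once, under vaccine dose 1 at Day 0. The row "Review of Inclusion/exclusion criteria" is marked at both dose visits, so eligibility is checked again at dose 2, on Day 90 ± 3.

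Arms and Interventions gives both arms a subcutaneous first dose. Arm 1 is described as subcutaneous for the first "vaccination then intradermal Qdenga for 2" (the second vaccination), and arm 2 stays subcutaneous. The arms are therefore identical until dose 2.

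Section 5.6 says: "All participants will receive the first dose subcutaneously as per standard practice, then be randomized to receive the second dose either subcutaneously or intradermally". It gives the order but no day.

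Two routes out of the trial between the doses matter here. Section 5.7.4 lists as a withdrawal reason: "The participant chooses to withdraw from the study at any time". Exclusion criterion 10 in section 5.7.3.2 covers inability to follow the protocol or understand the consent, in the researcher's "judgment, due to various medical, psychological, social or other conditions".

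No supplied text describes sequence generation, concealment, or when allocation is disclosed. The nearest statement, in section 5.7.10, is that laboratory and participant data are linked only at the end. It does not address who knows the arm. The Data analysis text names no analysis set and no rule for missing outcomes.

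**The concern.** Randomisation protects a comparison best when it happens as close as possible to the point where treatments diverge. Here the schedule leaves a gap of about three months in which the arms are treated alike but participants already belong to an arm.

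Two things follow. First, anyone who leaves in the gap has been randomised, never receives the dose under comparison, and has no Day 120 outcome. The plan does not say how such a person is counted. This holds whether or not the arm is known.

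Second, if participants or staff know the arm before Day 90, leaving may depend on it. A participant may decide not to return because of the planned route, or staff may apply a judgement-based criterion at the second eligibility review knowing what comes next. Loss that depends on both arm and likely response would bias the Day 120 comparison between intradermal and subcutaneous second doses.

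**Working it through.** **1. The gap.** Dose 2 falls on Day 90 ± 3 and the randomisation mark is at Day 0, so the gap is 87 to 93 days. If randomisation moves to the dose 2 visit, the gap is zero.

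**2. Is the mark an extraction error?** Six other rows have marks in both dose columns: eligibility review, physical examination, weight/height/vital signs, concomitant medication, blood collection and vaccination. The dose 2 column as a whole was not lost. This does not prove every single mark.

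**3. Sample size.** Section 5.7.6 gives 24 in total, 12 per arm: 2 × 12 = 24. It is a pilot rule of thumb with no effect size, SD or loss rate, so there is no further figure to reproduce. The 95% confidence interval half-width for a difference in means at 12 v 12 is t(0.975, 22) × √(2/12) = 2.074 × 0.408 = 0.85 SD.

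**4. Chance of at least one loss before dose 2.** The documents give no loss rate. Assume 5%, 10% or 20% among 24 randomised at Day 0:
- 1 − 0.95²⁴ = 71%
- 1 − 0.90²⁴ = 92%
- 1 − 0.80²⁴ = 99.5%

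**5. Bias if leaving depends on arm.** Assume k = 1, 2 or 3 of 12 leave one arm and nobody leaves the other. There are two ways to express how leaving relates to response, and they should not be confused.

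*(a) A latent tendency to leave correlates ρ with response.* The k with the strongest tendency leave. Bias = ρ × the mean of the remaining 12 − k expected normal order statistics = ρ × 0.148, 0.274 or 0.393.

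*(b) Leaving itself (yes or no) correlates r with response.* Bias = r × √(k/(12 − k)) = r × 0.302, 0.447 or 0.577.

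The link is r = ρ × 0.49, 0.61 or 0.68 for k = 1, 2 or 3. The same nominal correlation therefore means a larger bias under (b).

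| Bias in SD | k = 1 | k = 2 | k = 3 |
|---|---|---|---|
| latent ρ = 0.1 | 0.01 | 0.03 | 0.04 |
| latent ρ = 0.3 | 0.04 | 0.08 | 0.12 |
| latent ρ = 0.5 | 0.07 | 0.14 | 0.20 |
| leaving r = 0.1 | 0.03 | 0.04 | 0.06 |
| leaving r = 0.3 | 0.09 | 0.13 | 0.17 |
| leaving r = 0.5 | 0.15 | 0.22 | 0.29 |

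In a 400,000-run simulation, the nominal 95% interval covers 94.8%, 94.5% and 94.1% at latent ρ = 0.3, and 94.5%, 93.6% and 92.7% at latent ρ = 0.5.

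**6. What later randomisation does not remove.** Refusal after the route is disclosed at Day 90 remains possible. If 3 would have left and 1 still refuses, the bias at latent ρ = 0.3 falls from 0.12 to 0.04 SD, not to zero. If all 3 still refuse, nothing is gained on that route.

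**7. Why the list must be concealed.** The route is visible once given. If the block size is known, in a block of 4 the last allocation is always certain, and the third is certain when the first two agree (chance 1/3): (1 + 1/3)/4 = one third of allocations. In blocks of 2 it is one half. Staff could then anticipate the arm at the eligibility review, which is the exposure the change is meant to close.

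**The case against.** The strongest reply is that the bias needs the arm to be known before Day 90, and nothing says it is. The CONSORT and study-flow diagrams are not shown and might settle both timing and disclosure. Section 5.6 is compatible with randomisation at dose 2, so the plan may already intend what is proposed. The schedule is also a fragile anchor: it has no Day 30 blood mark although sections 5.6 and 5.7.8 require one, and no adverse event mark at dose 2. Finally, for a pilot seeking preliminary estimates, the assumed biases are small beside 0.85 SD.

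Most of this stands as a limit on strength. It does not remove the point. The only dated text says Day 0. If dose 2 was intended, the mark needs correcting; if Day 0 was intended, a disclosure rule is needed.

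A reader might infer three stronger things that the documents do not support:
- **That section 5.6 contradicts the schedule.** It does not: randomising on Day 0 after the injection satisfies both.
- **That participants would avoid the intradermal arm.** Section 5.5 reports that induration and pruritus "were more frequent following intradermal vaccination compared to subcutaneous administration", but adds: "Most of these reactions were mild and resolved within one day". It also cites a trial in which the difference in local events was not significant, and suggests that a reduced dose may have fewer side effects. The direction is open.
- **That later randomisation secures equal arms.** This depends on the method. With 5%, 10% or 20% loss, the chance that the arms differ by 2 or more is 14%, 29% or 44% when 12 + 12 are randomised at Day 0. At Day 90 it is 7%, 10% or 8% with blocks of 4, but 76%, 75% or 73% with simple randomisation. Arm size is not the reason for the change.

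**Conclusion.** The point holds as a design improvement. It is not evidence that the trial is biased, and a reader should not conclude that allocation is open from Day 0. Two parts differ in certainty. Randomising at Day 0 makes every exit before dose 2 a post-randomisation loss, whatever is disclosed. Arm-dependent loss arises only if the arm is known early. If it is sealed until dose 2, that bias before dose 2 does not arise.

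For 1 to 3 of 12 leaving one arm only, the bias is 0.04 to 0.12 SD at a latent correlation of 0.3, or about 0.09 to 0.17 SD if leaving itself correlates 0.3. The largest value in the range examined is 0.29 SD, about a third of the 0.85 SD half-width. The number leaving, the one-sided pattern and the correlations are all assumptions. The finding on disclosure is limited to the supplied text. Because the arms are identical until dose 2, randomising or unsealing then loses no information about the route comparison.

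**What to change.** Move the randomisation mark in the Study procedure table to the dose 2 visit, after eligibility is re-confirmed and immediately before the injection. State that day in section 5.6 so that the two places agree. Use blocked 1:1 randomisation, with the list and the block sizes (preferably varied) concealed from enrolling staff.

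Alternatively, keep a list drawn up at Day 0 but seal each allocation from participants and staff until that same moment, and say so.

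Under either option, count and report by arm anyone who declines after disclosure.

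The cost is one schedule mark and a few sentences. With later randomisation, the number randomised is known only at Day 90 and may fall below 24. To randomise 24 on average would take 24/(1 − loss) = 25.3, 26.7 or 30.0, so 26, 27 or 30 enrolled at an assumed 5%, 10% or 20% loss; the change does not require this. The sealed list keeps 24 randomised, but exits before dose 2 remain post-randomisation losses.
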